We have developed human laboratory cocaine self-administration procedures that have strong predictive validity for determining the impact of behavioral manipulations on cocaine taking. For example, we have shown that the availability of mutually exclusive alternative reinforcers reduces cocaine self-administration. This arrangement models another effective psychosocial intervention, contingency management. In this pilot study, our self-administration procedures will be adapted to evaluate the influence of decisional analysis/craving regulation features of CBT on cocaine self-administration, thereby determining how these components contribute to the ability of CBT to promote biologically verified cocaine abstinence.

The specific aim of this project is to demonstrate that the decisional analysis/craving regulation aspects of CBT reduce cocaine self-administration in subjects with cocaine use disorder through diminished craving responses. Thirty non-treatment seeking human subjects meeting diagnostic criteria for cocaine use disorder will complete an outpatient, crossover, placebo-controlled study consisting of 1 practice and 9 experimental sessions. In each experimental session, the reinforcing effects of intranasal cocaine (0, 40 or 80 mg) will be determined under one of three regulation of craving conditions that simulate CBT decisional analysis (i.e., negative instruction, positive instruction or a neutral “look” condition). After sampling the dose of cocaine available in each session, subjects will complete the craving manipulation assigned to that session, they will then rate their craving and finally they will have the opportunity to earn the sampled dose in a progressive-ratio procedure. We hypothesize that focusing on the negative effects of cocaine use will decrease craving and reduce cocaine self-administration relative to the positive and “look” conditions, and that craving will be positively correlated with self-administration outcomes.

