3. STUDY DESIGN

A double-blind, placebo-controlled, crossover design will be used in this experiment. A completely within-subject design will be used such that each subject will receive all possible dose conditions.

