7. RESEARCH PROCEDURES

General Procedures. Subjects that meet the inclusion criteria will participate as outpatients at the University of Kentucky LHBP and Clinical Services Core (CSC). Subjects will be discharged at the end of each day, provided that they meet release criteria.

This experiment will require each subject to complete a total of one practice and nine experimental sessions over approximately two to three weeks. Experimental sessions will be conducted as outlined in the table below. We would like to note that the order of the experimental sessions (i.e., dose tested and craving manipulations) will be randomized across subjects. The practice session will familiarize subjects with the experimental routine and tasks, but no drug will be administered and subjects will receive instructions on each of the craving manipulation conditions (positive, negative, and look [neutral]).

Time	
0800	Arrival at LHBP. Drug and alcohol use restriction compliance verified. Transport to CSC.
0900	Baseline craving, subjective-effect and physiological measures completed.
1000	Subject samples intranasal dose available for that session. Subjective-effect and physiological measures completed at 15-minute intervals for 45 minutes. Commodity purchase tasks completed 15 minutes after sampling dose.
1045	Subject completes regulation of craving manipulation assigned for that session (positive, negative or look) and rates craving.
1050	Subject offered opportunity to work for dose on progressive-ratio schedule.
1100	Dose administered, if earned and physiological measures are within acceptable limits.
1115	Subjective-effects and physiological measures completed.
1130	Craving manipulation, craving measurement, progressive-ratio procedure and subjective-effects and physiological measures sequence completed. Repeats 4 more times at 45-minute intervals.
1530	Discharge from CSC. Return to LHBP for final sobriety testing, payment and release.
Note	Cocaine dose and craving manipulation will be presented in random order. A fully factorial design will be used so that all possible combinations are tested once each over nine sessions.

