During the actual manipulation in experimental sessions, subjects will be presented 30 trials depicting cocaine images. Each trial will begin with an instruction presentation (i.e., positive, negative, look) followed by 6-second image presentation. The instruction presentation will remain constant within each experimental session. Images will be presented in random order from a bank of 300 images to minimize habituation. After each image offset, subjects will rate craving for cocaine using a 0-10 visual analog scale (0 = Not at All; 10 = Very Much) (Lopez et al., 2015). Craving, averaged across all trials in a session, will be the primary outcome. The manipulation will be repeated prior to each self-administration opportunity.

Progressive-Ratio Procedure. Following a 30-image trial, subjects will be offered the opportunity to earn the sampled cocaine dose on the Progressive-Ratio Procedure. We have a long history of using this procedure to assess the reinforcing effects of stimulant drugs ([name], 2008), including cocaine ([name] et al., 2010a; 2012a). It yields orderly, dose-related self-administration outcomes. Subjects will have a total of five opportunities to earn the dose they sampled at the outset of the session in order to provide multiple replication trials to determine the impact of the craving manipulation on drug self-administration (Ferster and Skinner, 1957; Spiga and Roache, 1997). The initial response requirement for a dose will be 400 mouse clicks. Response requirements will increase by 200 for each subsequent dose. For example, if a subject chooses cocaine at the first trial, earning that dose would require 400 responses. At the second opportunity, if he/she chooses to earn cocaine again, earning that dose would require 600 responses. If he or she elects not to earn cocaine at any given opportunity, the response requirement would not increase for the next opportunity. If a subject were to choose cocaine across all opportunities, the response requirements would be 400, 600, 800, 1000 and 1200 responses. The primary outcome is the number of cocaine doses earned.

Subjective-Effects and Physiological Measures. A subjective-effects questionnaire and physiological measures will also be used to assess cocaine effects and monitor safety.

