Data Analysis. All data will be analyzed using SPSS (IBM Corporation, Armonk, NY). To test our primary hypothesis, self-reported craving scores and number of cocaine doses earned will be analyzed using two-factor repeated-measures General Linear Model (GLM) with data from the 30 subjects who complete the protocol. The α level will be set at $p \leq 0.05$. Data from subjects who do not complete will not be included in the analyses. Cocaine Dose (0, 40 and 80 mg) and Craving Manipulation (positive, negative and look) will be the factors of the ANOVA. A significant change in craving or self-administration will be inferred if the Interaction of Cocaine Dose and Craving Manipulation attains statistical significance. If the interaction attains statistical significance, the mean square error term will be used to conduct Tukey's HSD post-hoc test to make appropriate pair-wise comparisons. If baseline measures (e.g., craving) differ across conditions, they will be entered into the analysis as covariates. To test our secondary hypothesis, craving scores will be averaged for each of the nine conditions and compared with self-administration outcomes using Pearson correlations. Subjective-effect and physiological data following the sampling dose will be averaged across craving manipulation conditions because they will be collected prior to the craving manipulation and analyzed using cocaine dose and time as factors in a repeated-measures GLM. Exploratory analyses considering relevant biological variables (i.e., sex, age and race/ethnicity) will also be conducted.

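### The Pearson correlations for the secondary hypothesis name no unit and carry no subject, dose or manipulation term, so they cannot show that intake falls through craving

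*Combined protocol and SAP*

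**What the plan says.** The Background states the aim as a mechanism: the craving manipulation should "reduce cocaine self-administration in subjects with cocaine use disorder through diminished craving responses". The hypothesis that goes with it is weaker, that "craving will be positively correlated with self-administration outcomes".

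The design is crossed within subjects. Section 3 says "A completely within-subject design will be used such that each subject will receive all possible dose conditions", and the note to the session table in section 7 says "A fully factorial design will be used so that all possible combinations are tested once each over nine sessions".

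On the craving measure, section 7 says "Craving, averaged across all trials in a session, will be the primary outcome". The self-administration measure is the number of doses earned, 0 to 5 per session. Of the progressive-ratio procedure the same section says "It yields orderly, dose-related self-administration outcomes".

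The secondary analysis is one sentence in Data Analysis: "craving scores will be averaged for each of the nine conditions and compared with self-administration outcomes using Pearson correlations". Dose and manipulation are named as factors for the ANOVA only. The covariate rule there concerns baseline measures that differ across conditions. It supplies no subject, dose or manipulation term for the correlations.

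**The concern.** The sentence fixes the level at which craving is averaged, but not the unit of the correlation, the number of pairs, or how several correlations would be combined. The plural form does not settle it. Four readings fit:

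- (i) one correlation over nine condition means;
- (ii) one correlation over all subject-by-condition pairs;
- (iii) nine correlations, one per condition, across subjects;
- (iv) one correlation per subject, over that subject's nine conditions.

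A link between craving and intake can be mimicked in two ways. Some people crave more and also take more. And the randomised factors can move both variables. Dose is expected to move intake, and craving is rated from 45 minutes after the sampled dose, so dose is a common cause as soon as it also shifts craving. None of the four readings separates the link from both sources.

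This is the only planned analysis that connects craving with drug taking; the repeated-measures GLM tests each outcome on its own. Any statement that craving is the route therefore rests on this sentence.

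**Working it through.** **Inputs from the documents.** 3 doses × 3 manipulations = 9 conditions; 30 completers; 30 × 9 = 270 pairs; alpha 0.05, taken here as two-sided because the plan does not say. The plan gives no expected correlation, standard deviation or power for this analysis, so there is no stated figure to reproduce.

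**Assumptions, not in the documents.** Total SD 1 for each variable; intraclass correlation (ICC) 0.5, with 0.3 to 0.7 as the range; dose effects linear and expressed from 0 to 80 mg; dose raises intake by 1 SD. Rates not derived by formula come from simulation (10,000 replicates per scenario).

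**1. Pooled pairs (ii), no effects of any kind.** The variance of r is inflated by about 1 + (9 − 1) × ICC², so the rejection rate is about 2[1 − Φ(1.96/√(1 + 8·ICC²))].
- ICC 0.3: 1 + 8 × 0.09 = 1.72, rate 13%.
- ICC 0.5: 1 + 8 × 0.25 = 3.00, rate 26%.
- ICC 0.7: 1 + 8 × 0.49 = 4.92, rate 38%.

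Simulation gives the same values, split evenly by sign.

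**2. Nine condition means (i).** The critical |r| with 7 df is 2.365/√(2.365² + 7) = 0.666. Each mean carries noise variance 0.5/30 = 0.0167, or 0.0148 after the factor 8/9. A dose effect d contributes d²/6.
- Intake, d = 1: 0.1667/(0.1667 + 0.0148) = 0.918.
- Craving, d = 0.3: 0.0150/(0.0150 + 0.0148) = 0.503, so r is about √(0.918 × 0.503) = 0.68.
- Craving, d = 0.5: 0.0417/(0.0417 + 0.0148) = 0.738, so r is about √(0.918 × 0.738) = 0.82.

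Both exceed 0.666 although no subject has any craving-intake link beyond dose.

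**3. Nine correlations of 30 subjects (iii).** Each test is valid and free of dose. If independent, at least one of nine is significant in 1 − 0.95⁹ = 37%; simulation at ICC 0.5 gives 34%.

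**4. Readings side by side.** Significant positive results with no within-person link, when dose raises craving by 0.3 / 0.5 SD (range over ICC in brackets):

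| Reading | Rate | What it leaves in |
|---|---|---|
| (i) nine means | 62% [46–84] / 95% [85–100] | dose and manipulation |
| (ii) 270 pairs | 22% [17–28] / 34% [28–37] | person, dose, manipulation; independence violated |
| (iii) nine of n = 30 | unaffected by dose | person only; no multiplicity rule |
| (iv) per subject | 28% [17–56] / 61% [38–94] | dose and manipulation; no combining rule |
| Subject and nine conditions removed | 2–3% | – |

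The last row has 270 − 30 − 8 − 1 = 231 df. If dose does not move craving, (i) and (iv) return to 2–3%.

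**5. Link between persons only.** With a between-person correlation of 0.3 / 0.5, (ii) is significantly positive in 57% / 87%, and (iii) has at least one positive result in 57% / 84%. The adjusted analysis stays at 2.5%.

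**6. A true within-person correlation of 0.2, dose not moving craving.** Power is 3% for (i), 40% for (ii), 8% per test for (iii), 67% for (iv) and 86% for the adjusted analysis.

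**7. Timing.** There are 30 ratings before each of five opportunities, 150 in all, and 150 − 30 = 120 come after the first opportunity. The session table says "Dose administered, if earned and physiological measures are within acceptable limits", so an earned dose that is given could change later craving. If each administered active dose shifted later craving by 0.1 / 0.2 SD and 70–100% of earned doses were given, even the fully adjusted analysis would be significant in that direction in 12–19% / 32–58% with no effect of craving on intake. The real size is unknown.

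**The case against.** The strongest reply is that the hypothesis as worded asks only for a positive correlation, and a Pearson correlation estimates one. If dose moves both variables, the condition means do covary; if heavy cravers take more, that link is real. For the marginal association alone, only the pooled reading is invalid. This stands. It limits the point to the unstated unit, the repeated measures, and the step from association to mechanism.

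The readings are also not equally natural: one correlation per subject needs a combining step that the text never mentions. That stands too, but dropping it rescues none of the others.

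The work is described as a pilot and the analysis is secondary. That bears on weight. The sentence is still the plan's test of a hypothesis.

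Three stronger readings are tempting and are not supported:

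- **That analysts following the plan would reach opposite conclusions.** Significant results of opposite sign among (i), (ii) and (iv) occur in about 0.3–4% of simulated trials. They reach about 14% only if dose lowers craving by 0.5 SD while raising intake by 1 SD, which nothing in the documents suggests. The usual disagreement is over whether the result is significant.
- **That covariation produced by the manipulation is a false positive.** If the manipulation moves both outcomes by 0.5 SD, condition means are significantly positive in 77% of trials. The Background predicts that pattern. It does not tell a route through craving from two parallel effects, so it should be modelled, not scored as an error.
- **That craving from the first block must replace the session mean.** That would discard 120 of 150 ratings and depart from the plan's defined measure. It is a trade-off and belongs in a sensitivity analysis.

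**Conclusion.** The point holds, and should be fixed. What is certain from the text is that the correlations have no stated unit and no subject, dose or manipulation term in a nine-session within-subject design, and that no reading removes both between-person differences and the randomised factors. A marginal correlation can meet the literal hypothesis. It cannot support the aim's statement about the route.

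The sizes are conditional. The 26% for pooled pairs depends only on the assumed ICC (13–38%). The rates for condition means and per-subject correlations also require dose to move craving, on which the documents give no figure; without that they are nominal. Confidence is high in the omission and lower in its numerical consequence.

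A reader might infer that the trial's main result is compromised. It is not: the GLM analyses of craving and of doses earned do not use these correlations.

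**What to change.** Replace the Pearson correlations with a mixed model of doses earned. Fixed terms: within-subject-centred session-mean craving, subject-mean craving, dose, manipulation and dose-by-manipulation. Include a random subject effect, and use subject-clustered standard errors as a check. Report the within-subject craving coefficient as the craving-intake association.

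Base any statement that intake falls through craving on a within-subject mediation analysis that keeps the manipulation contrast, and state that craving itself is not randomised. Otherwise claim association only.

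For reverse influence, add a sensitivity analysis with first-block craving, or pair each block's craving with the choice that follows it. Keep raw correlations as descriptive, with the unit stated.

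The cost is wording and programming; no new data are needed. Under the assumptions above, power with session-mean craving is about 87% at a within-person correlation of 0.2, 80% at about 0.18, and 76–80% at 0.2 when intake is a 0–5 count. First-block craving lowers the 87% to 53–77% if intake tracks the session mean and 30–70% of within-subject craving variance is shared across blocks. If the craving slope varies between subjects (SD 0.2–0.3), the random-intercept model rejects in 8–12% with no average link, against about 6% with clustered errors, which is the reason for that check. The sponsor must also accept that the adjusted result may look less favourable than a raw correlation.

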Subjects will be encouraged to abstain from illicit drugs for the duration of the study and from alcohol for the 12 hours prior to, and following, each experimental session. They must also agree to abstain from solid food and caffeine for 4 hours before each experimental session. Subjects will arrive at the LHBP at approximately 0800 hours. Upon arrival at the LHBP, a breathalyzer and a field sobriety test will be conducted, a urine sample collected, and pre-session paperwork completed. A breathalyzer positive for alcohol or a urine sample positive for recent use of amphetamines, benzodiazepines, barbiturates, or opioids will preclude the subject from participation in the session. If a subject tests positive for recent use of cocaine or marijuana (THC), [name] or [name] must be notified. Subjects will only be allowed to participate in a session with a marijuana or cocaine positive urine if they pass the sobriety testing and baseline cardiovascular measures are within acceptable limits (i.e., heart rate < 90 bpm, if systolic pressure < 140, or diastolic pressure < 90). Moreover, intranasal cocaine doses may not be administered until two hours following all subjects' arrival, regardless of the outcome of their urinalysis. Subjects will then be provided with a standard, fat- and caffeine-free breakfast. Prior to beginning each experimental session, subjects that report smoking tobacco cigarettes will be allowed to smoke one cigarette.

At 0830, subjects will be transported to the CSC. Physiological measures will be recorded at 15-minute intervals upon arrival at the CSC. At 1000, subjects will sample the dose of intranasal cocaine available that day (0, 40 or 80 mg). After sampling the drug, subjects will complete the subject-rated measures. Subjects will then make 5 choices to self-administer the sampling dose after completing the craving manipulation. Choices will be separated by 45 minutes. Drug administration will be withheld if heart rate > 90 bpm, if systolic pressure > 140 or

diastolic pressure > 90. Subjects will be excluded from further research participation if at any time during an experimental session heart rate increases above 130 bpm, diastolic pressure increases above 110 mmHg or systolic pressure above 180 mmHg.

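### The sampling-dose model for heart rate, blood pressure and temperature does not clearly use each session's pre-dose readings, which costs precision in a secondary analysis but does not bias it

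*Combined protocol and SAP*

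**What the plan says.** All the relevant text is in section 7, Research Procedures.

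- **The model.** The last part of the Data Analysis paragraph states: "Subjective-effect and physiological data following the sampling dose will be averaged across craving manipulation conditions". The reason given is that these data precede the craving manipulation. They are then "analyzed using cocaine dose and time as factors in a repeated-measures GLM". The sentence names no baseline covariate, change score or pre-dose time level.
- **Post-dose readings.** The session table has "Subjective-effect and physiological measures completed at 15-minute intervals for 45 minutes", which gives three post-dose points.
- **Pre-dose readings.** The 0900 row of the same table reads "Baseline craving, subjective-effect and physiological measures completed". General Procedures adds: "Physiological measures will be recorded at 15-minute intervals upon arrival at the CSC". The sampling dose follows at 1000.
- **Baseline rule.** Earlier in the Data Analysis paragraph, after the primary model and before the secondary hypothesis, the plan says: "If baseline measures (e.g., craving) differ across conditions, they will be entered into the analysis as covariates".
- **Design.** The note to the session table says "Cocaine dose and craving manipulation will be presented in random order" and that "all possible combinations are tested once each over nine sessions". With three doses and three manipulations, each dose is given in three sessions.

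**The concern.** Subjects attend as outpatients. They may take part with cocaine- or THC-positive urine if they pass sobriety testing and their cardiovascular values are within limits, and smokers may have one cigarette before the session. Starting heart rate and blood pressure can therefore differ from one session to the next within a subject. If the model ignores the pre-dose readings, that variation goes into the subject-by-dose error against which the dose effect is judged.

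At stake is how precisely the trial describes cocaine's physiological effects. The readings that could improve it are already being collected.

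**Working it through.** The documents give no standard deviation, effect size, power or pre/post correlation for these measures, so there is no stated figure to reproduce. The size has to be shown over a range of assumptions.

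**Inputs.** From section 7: n = 30 completers, k = 3 sessions averaged per dose, alpha 0.05 (taken as two-sided). Assumed: session-to-session SD within subject s, equal before and after dosing, and r, the within-subject correlation between pre-dose and post-dose readings. Here r is taken as 0.3, 0.5 and 0.7, with 0.8 added in the simulation.

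**Step 1: variance of a dose difference, if subjects share the same true dose response.**
- Unadjusted: 2s²/(nk) = 2s²/90.
- Adjusted for the pre-dose value: 2s²(1 − r²)/90.
- Change from baseline: 2s² × 2(1 − r)/90.

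| r | Adjusted variance, 1 − r² | Narrower interval, 1 − √(1 − r²) | Equivalent completers, 30/(1 − r²) | Change-score variance, 2(1 − r) |
|---|---|---|---|---|
| 0.3 | 0.91 (−9%) | 5% | 33 | 1.40 |
| 0.5 | 0.75 (−25%) | 13% | 40 | 1.00 |
| 0.7 | 0.51 (−49%) | 29% | 59 | 0.60 |

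With s = 8 units (assumed), the standard error of a dose difference is 8 × √(2/90) = 1.19 unadjusted, and 1.14, 1.03 and 0.85 adjusted. Averaging three sessions reduces the absolute noise but leaves the proportional gain unchanged, because pre-dose and post-dose values are averaged alike.

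**Step 2: bias or precision?** A paired comparison of two doses was simulated with these inputs (4,000 runs per setting, r from 0.3 to 0.8). With no dose effect, the unadjusted analysis rejected in 4.6–5.2% of runs. With a true difference of 3 units, its mean estimate was 2.98–3.01. It is therefore unbiased with correct type I error.

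**Step 3: does the conditional rule recover the loss?** The rule was read as adjusting only when pre-dose values differ at p < 0.05. Power for the 3-unit difference was:
- unadjusted: 67–69%
- conditional rule: 68–70%
- always adjusted: 70% (r = 0.3) to 98% (r = 0.8)

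Type I error under the conditional rule was 3.2–4.4%. In addition, a covariate in a standard repeated-measures GLM takes one value per subject, so it cannot adjust each dose mean by its own pre-dose value.

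**Step 4: individual dose response.** Baseline cannot explain real differences between subjects in how they respond to a dose. Suppose the true dose difference varies between subjects with SD equal to s. The variance of one subject's dose difference is then 2s²/3 + s² = 5s²/3, of which only 2/5 is session noise. The reduction becomes 0.4r² = 3.6%, 10% and 19.6%. Simulation of this case, which includes the cost of estimating the slope, gave about 0%, 10% and 16%.

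**Step 5: form of the covariate.** The 1 − r² gain requires the within-subject slope. With the covariate centred within subject and a common dose response, simulated variance ratios were about 0.89–0.96 at r = 0.3, 0.73–0.77 at 0.5 and 0.49–0.56 at 0.7. An uncentred covariate mixes between-subject and within-subject associations. With between-subject SD 8–12 and between-subject correlation 0.9–1.0 (assumed), it raised the variance by 8–12% at r = 0.3 and lowered it by only 9–17% at r = 0.5.

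**The case against.** The strongest reply is that the plan already has a baseline rule. It speaks of baseline measures in the plural, gives craving only as an example, and the 0900 row lists physiological measures as part of the baseline. This stands in part: it cannot be said that the plan ignores baseline. However, the rule follows the primary model and refers only to the analysis, so its reach is unclear, and step 3 shows that it would recover little.

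A second reply is that the design already controls the problem. Order is randomised, three sessions are averaged per dose, and cardiovascular limits and a two-hour wait after arrival narrow the starting range. This also stands, and it rules out a stronger reading. A reader might infer that differences in starting values distort the dose comparison. The documents do not support that: under randomised order these differences are chance, and step 2 shows no bias.

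A third reply is that r is assumed and the gain may be small. That is correct. The percentages in step 1 are upper limits unless r is already net of individual differences in dose response.

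Finally, these measures assess cocaine effects and monitor safety. They serve neither the primary objective nor the correlation hypothesis.

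**Conclusion.** The point holds as a minor matter of precision. The sampling-dose model does not clearly use the pre-dose readings, and the conditional rule is neither clearly applicable nor effective here. For assumed r of 0.3, 0.5 and 0.7, error variance could fall by at most about 9%, 25% and 49%. It falls by less if true dose response varies between subjects: about 0%, 10% and 16% when that SD equals the session SD. None of r, s or the dose-response SD is in the documents.

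A reader might also infer that the craving and doses-earned results are affected. They are not, because those outcomes are analysed in a separate model.

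**What to change.** In the Data Analysis text, replace the conditional rule for this model with adjustment that applies in every case:

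- For heart rate, blood pressure and temperature, take the mean of the session's pre-dose readings, averaged over the three sessions at each dose as the post-dose data are.
- Enter it as a dose-varying covariate centred within subject, with the subject mean as a separate term if wanted, in a mixed model with dose, time and dose-by-time.
- Leave the drug-effect questionnaire unadjusted, because its items (Appendix A) ask about a drug that has not yet been given at baseline.
- State which analyses the existing baseline rule still covers.

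A change score is not a safe substitute: it raises the variance by 40% at r = 0.3 and helps only when r exceeds 0.5. Adding baseline as a fourth time level would dilute the dose main effect to three quarters, since one of four points would carry no drug effect.

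The cost is a wording change, one extra model term and a mixed model in place of the GLM. No new data are needed. If the correlation is low, there is little or no gain.
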